For testing in all settings, WHO recommends testing focused on persons with signs and symptoms of chronic liver disease and groups with a high prevalence of HCV infection. However, if the prevalence of infection in the general population exceeds 2-5%, WHO recommends testing in the general population (19). WHO recommends treatment with pangenotypic direct-acting antivirals (DAAs) for all adults with chronic hepatitis C infection. In Colombia, according to data from the high-cost account, the currently available DAA sofosbuvir/velpatasvir achieves an efficacy of 98.7% of HCV-infected patients, and a treatment duration of 12 weeks (9).

Early diagnosis of infection and linkage to treatment is one of the priority lines of action. Policies on HCV screening should be articulated in different settings (24). Key issues impeding HCV elimination are the lack of reliable and up-to-date estimates of active HCV infections and related disease burden (21).

The WHO strategy defines ambitious targets to eliminate HCV as a public health threat by 2030, to achieve which the scale-up of DAA treatment is essential, but this is a huge public health challenge. Identification of patients who are unaware of their HCV status represents the main barrier to be overcome, by 2017 according to WHO report only 20% of people with HCV worldwide had been diagnosed (6). Micro-elimination strategies targeting small fractions of the population, as opposed to nationwide elimination programs, have shown improvement in diagnosis and treatment rates resulting in great benefits in expanding the HCV care cascade and achieving WHO targets (21).

According to the epidemiological situation of HCV infection in the general population and the most affected populations, and of the hepatitis C approach plans, the clinical guidelines of countries such as Spain, United Kingdom, Germany, France, Ireland, Canada or Australia

recommend population and opportunistic screening, i.e. HCV screening of persons with exposures and risk situations for infection such as injecting and/or inhaled drug use, risky sexual intercourse, HIV/HBV co-infection, cosmetic procedures performed with sharps without proper safety precautions, admission to correctional facilities (24), anyone who received blood transfusions before HCV serological testing of blood donors was initiated, who received medical or dental interventions in health care settings with substandard infection control practices (25).

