The indications for HCV screening by risk exposures instead of population screening allow focusing efforts and resources, responding to the principle of equity in the design, implementation, and evaluation of HCV screening programs in different territories, which allows addressing the barriers to access and use of services in each context (24). Targeted screening would identify a high rate of infected subjects, due to the higher rate of infection related to risk factors, and simultaneously reduce viral transmission by allowing HCV to be eliminated from individuals at higher risk of spreading the infection (26).

The results of the study by Rosato, et al (2022) indicate that opportunistic hospital screening in patients with various comorbidities is a feasible strategy to diagnose and then easily link infected patients to care. They also clearly show the need for increased awareness among general practitioners and other health care specialists, who care for patients with different comorbidities, to address HCV disease management. This is also important because HCV eradication has been shown to significantly improve not only liver disease outcomes but also various comorbidities, such as cryoglobulinemic vasculitis, diabetes, cardiovascular and renal diseases, etc. (27).

Care cascade monitoring (CoC) is an important component of the response to the global hepatitis C virus (HCV) epidemic. The function of a CoC is to represent how many members of a population have progressed through each stage in a sequence of stages required for effective disease control: e.g., diagnosis, treatment, and cure; the findings obtained will enable health system decision-makers to determine where the greatest gaps are in testing, linkage to care, and treatment among persons with chronic HCV infection (28).

A hospital-centered HCV micro-elimination approach provides a framework for expanding linkages to care and treatment on the path to achieving WHO's 2030 targets (21). It is less complex and costly than large-scale national efforts to eliminate HCV, and it can build

momentum by producing small victories that inspire more ambitious efforts (6). Fragile populations require dedicated screening and integrated care programs, which can begin in hospitals and continue in a network involving all processes including telehealth (21), promoting the adoption of new models of care in specific populations (6).

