4.1 General objective

To determine the prevalence of HCV in patients with risk factors for HCV captured through opportunity screening in the hospital institutions included.

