5.2 Study population

All persons over 18 years of age who are treated in the included health care institutions (IPS) and who are users of hospitalization, emergency, outpatient and any other hospital care services.

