5.3 Inclusion criteria

Have at least one of the following risk factors for hepatitis C.

- Over 50 years of age with no risk factors.
- Over 18 years old and < 50 years old, with risk factors for hepatitis C:
 - ✓ Persons who have received medical or dental interventions in health care settings.
 - ✓ Persons who have had tattoos, body piercings, or scarification procedures.
 - ✓ Persons with HIV or hepatitis B infection.
 - ✓ Persons who inject drugs.
 - ✓ Persons who have used intranasal drugs.
 - ✓ Persons deprived of liberty and previously incarcerated persons.
 - ✓ Anyone with abnormal liver tests or liver disease.
 - ✓ Students, health care workers, or members of public safety (e.g. correctional

service officers or police) who have come into contact with blood at work through needlestick or sharps injuries.

- ✓ Anyone who has undergone hemodialysis.
- ✓ Persons who received transfusions in Colombia before 1996.
- ✓ Persons with comorbidities potentially associated with CH: diabetes, ischemic heart disease, cryoglobulinemia, chronic renal failure, Sjögren's syndrome, hypothyroidism, lichen planus, rheumatoid arthritis, HIV, non-Hodgkin's lymphoma, acute lymphoblastic leukemia, waldenstrom's macroglobulinemia.
- Individuals previously treated for HCV with sustained viral response in whom reinfection is suspected (individuals who continue to engage in risk behaviors)
- Accept to participate in the study by signing the informed consent form.

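### The under-50 entry line on medical or dental care, together with age-only entry over 50, means the pooled prevalence is not a prevalence in patients with risk factors

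*Combined protocol and SAP*

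**What the plan says.** The general objective (Section 4.1) is "To determine the prevalence of HCV in patients with risk factors for HCV captured through opportunity screening", and the research question in Section 3 has the same target. Section 2 gives the reason for selecting on risk: "Targeted screening would identify a high rate of infected subjects, due to the higher rate of infection related to risk factors".

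Section 5.2 takes the study population to be adults treated at the participating institutions, "who are users of hospitalization, emergency, outpatient and any other hospital care services". Section 5.7 enrols eligible patients consecutively, as a convenience sample, until the target number is reached.

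Section 5.3 opens with "Have at least one of the following risk factors for hepatitis C". Two of the routes beneath it matter here:

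- Under 50, any one factor on a list is enough. The first factor is "Persons who have received medical or dental interventions in health care settings", with no limit on procedure, date or setting.
- Over 50, the wording is "Over 50 years of age with no risk factors".

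In summarising other countries' guidelines, Section 2 describes the medical and dental exposure more narrowly, as people "who received medical or dental interventions in health care settings with substandard infection control practices".

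Section 5.10 plans frequencies and percentages, and chi-square tests of each risk factor against antibody positivity. It plans no prevalence restricted to participants with a specific factor and does not mention confidence intervals.

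**The concern.** In the background, what makes medical or dental care a risk factor is the poor infection control. Without that limit, the criterion describes something most people being treated in a hospital are likely to have had. If it is applied literally, the other under-50 factors no longer restrict entry. The term intervention is not defined, so each of the seven institutions must decide what counts, and case mix could differ between sites for reasons unrelated to HCV.

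What is at stake is the meaning of the main result. A figure reported as prevalence in people with risk factors would mix people with specific exposures, under-50s whose only factor is past care, and over-50s admitted on age. The mixing proportions would be unknown and might vary by site.

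**Working it through.** **1. Does the line select?** Entry needs one factor (5.3), the source is people already under hospital care (5.2), and eligible patients are taken consecutively (5.7). Read literally, the unqualified line admits most under-50 users. The documents give no proportion, so this is an inference from the wording.

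**2. Can entry routes be separated with the planned data?** I compared Section 5.3 with Table 1 of Section 5.5 and with Annex 1.

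- Recorded individually in both: transfusion before 1996, injected drugs, intranasal drugs, hepatitis B, HIV, tattoos or piercings, incarceration, liver disease, occupational blood exposure, hemodialysis.
- Medical or dental interventions: no item in either. The nearest is major surgery, which is not an entry criterion in 5.3.
- Comorbidities: Table 1 has one composite yes/no. Annex 1 has boxes for diabetes, cryoglobulinemia, coronary artery disease and renal failure. It has none for hypothyroidism, Sjögren's syndrome, lichen planus, rheumatoid arthritis, lymphoma, leukemia or Waldenström's macroglobulinemia.

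Prevalence among people with at least one recorded specific factor is therefore computable. The remainder is not a clean group: on Annex 1, an under-50 patient eligible through hypothyroidism looks the same as one admitted only by the medical or dental line.

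**3. Is the sample size affected?** Section 5.8 uses N = 280,186, p = 0.5, d = 0.05, design effect 3 and 95% confidence:

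n = 3 × 280,186 × 0.25 / [(0.0025 / 1.96²) × 280,185 + 0.25] = 210,139.5 / 182.593 = 1,150.86, rounded up to 1,151.

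This reproduces the stated minimum per institution. Neither p nor N depends on the disputed line, so rewording it leaves 1,151 unchanged.

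**4. Direction of the dilution (illustration).** Let f be the share of under-50 participants with a specific factor, pR their prevalence, and p0 the prevalence in the rest. Then pooled = f × pR + (1 − f) × p0. The introduction gives a national prevalence of 0.67%, and using it as p0 for hospital users under 50 is an assumption. The documents give neither f nor pR.

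| Assumed pR | f = 0.75 | f = 0.50 | f = 0.25 | f = 0.10 |
|---|---|---|---|---|
| 1% | 0.918% | 0.835% | 0.753% | 0.703% |
| 2% | 1.668% | 1.335% | 1.003% | 0.803% |
| 5% | 3.918% | 2.835% | 1.753% | 1.103% |

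For example, 0.50 × 2% + 0.50 × 0.67% = 1.335%. Across the grid the pooled value runs from 22% of pR (1.103/5) to 92% (0.918/1). If pR is close to p0 there is almost no dilution.

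**5. Precision of a restricted estimate.** For a subgroup that is a share g of one institution's 1,151, the 95% half-width is 1.96 × √[3 × p(1 − p) / (1,151g)].

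| Assumed p | g = 1 | g = 0.50 | g = 0.25 |
|---|---|---|---|
| 50% | 5.0 points | 7.1 | 10.0 |
| 2% | 1.4 points | 2.0 | 2.8 |

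At 2% and g = 0.50 the half-width equals the prevalence, so this normal approximation no longer serves and an exact or score-type interval would be needed for a single site. Separate estimates are possible but noticeably less precise.

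**The case against.** A reader might infer that every hospital user under 50 qualifies, so that risk selection is void. The documents do not show that. Intervention is undefined, and an outpatient visit need not include one. Table 1 lists major surgery among the risk factors although 5.3 has no surgery criterion, which may hint at a narrower intended meaning. The documents do not say so, and that reading would leave out dental exposure.

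A reader might also infer that the study cannot give a risk-group prevalence at all. That is too strong: most specific factors are recorded for each patient, so the restricted estimate can be computed. What is missing is the plan to report it and a clean way to isolate the other routes.

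Nor do the documents show that a qualifier was dropped by mistake. The narrower wording in Section 2 summarises foreign guidelines and is not this study's eligibility definition, so the broader line may be deliberate.

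A further defence is that 5.3 defines its own list, age over 50 included, as the risk factors, so that everyone enrolled has one by definition. This does not sit with the text, which describes the older group as having no risk factors, or with the rationale of a higher infection rate linked to such factors.

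Finally, the study is a single descriptive sample with no separate under-50 result planned, so rewording one line would not by itself cure the headline figure. That stands, and it is why reporting by entry route matters more than the wording.

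**Conclusion.** The point holds as a mismatch between the entry rules and the stated objective, and it should be fixed. Read literally, the medical or dental line gives little or no risk selection under 50, and age-only entry removes it over 50. The pooled prevalence describes hospital users who met broad entry criteria, not patients with risk factors.

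The size of the effect is unknown. The range of 22% to 92% rests on assumed shares (0.10 to 0.75), assumed risk-group prevalences (1% to 5%) and the national 0.67% applied to everyone else under 50. It shows direction only and concerns the under-50 stratum, for which no separate prevalence is planned. Individual test results and the sample size of 1,151 are not affected.

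**What to change.** 1. Reconcile Section 5.3 with Section 2: either restore the infection-control qualifier or define the exposure operationally, so that all seven institutions apply one rule. If the broader line is intended, say so and explain why.
2. Add to Table 1 of Section 5.5 and to Annex 1 a field recording every qualifying criterion met, including the medical or dental line and each listed comorbidity.
3. In Section 5.10, pre-specify prevalence with confidence intervals separately for (a) participants with at least one specific recorded factor, (b) under-50s admitted only on the medical or dental line, and (c) over-50s admitted on age alone. State which recorded items count as specific, since major surgery and sex between men are recorded as risk factors but are not entry criteria in 5.3.
4. Label the pooled figure as prevalence among screened hospital users meeting the entry criteria.

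The cost is one form amendment that needs ethics review at the institutions, a little more analysis, and wider intervals within each group. If the qualifier is restored, under-50 recruitment may slow. The 280,186 in Section 5.8 counts all people served, so it does not show how much. For anyone enrolled before the change, group (a) can still be reported, while groups (b) and (c) can be approximated only from the items recorded.

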	Inhaled or intranasal drug use	Having consumed inhaled drugs at any time.	0. No 1. Yes	Nominal, dichotomous
	Men who have sex with men	Man who has had sex with men.	0. No 1. Yes	Nominal, dichotomous
	Known hepatitis B virus infection	Refer to have a diagnosis of hepatitis B virus.	0. No 1. Yes	Nominal, dichotomous
	Known HIV infection	Refer to HIV diagnosis.	0. No 1. Yes	Nominal, dichotomous
	People who have had tattoos, body piercings, scarification, etc.	Presence of tattoos or piercing or scarification.	0. No 1. Yes	Nominal, dichotomous
	Population deprived of liberty or previously incarcerated persons	Being or having been deprived of liberty in a penitentiary center.	0. No 1. Yes	Nominal, dichotomous
	Liver disorders or disease	A person with abnormal liver	0. No 1. Yes	Nominal, dichotomous

Category	Variable name	Conceptual definition	Operational definition	Measuring scale
		tests or liver disease.		
	Occupational exposure	Healthcare workers or members of public safety (e.g., correctional service officers or police) who have been in contact with blood at work through needlestick or sharps injuries.	0. No 1. Yes	Nominal, dichotomous
	Hemodialysis	A person who has undergone hemodialysis.	0. No 1. Yes	Nominal, dichotomous
	Comorbidities potentially associated with HCV infection.	Diabetes, Ischemic heart disease, Cryoglobulinemia, Chronic renal failure, Sjögren's syndrome, Hypothyroidism, Flat lichen, Rheumatoid arthritis, Non-Hodgkin's lymphoma, Acute lymphoblastic leukemia, Waldenstrom's macroglobulinemia, Chronic renal insufficiency, Sjögren's syndrome	0. No 1. Yes	Nominal, dichotomous
Missed opportunity	Doctor visits	Doctor visits in the last month	How many?	Continued
Sample results	HCV antibody screening test	Report of HCV antibody test result.	0. Non-reactive 1. Reactive	Nominal, dichotomous
	Viral load test	Report the viral load result of those patients who presented reactive HCV antibodies.	0. Non-reactive 1. Reactive	Nominal, dichotomous

Category	Variable name	Conceptual definition	Operational definition	Measuring scale
Follow-up	SIVIGILA Report	The confirmed cases of HCV as a public health event are reported to the surveillance system utilizing form 340.	0: Not reported 1: If reported	Nominal, dichotomous
	Follow-up of confirmed case	Follow-up that each case confirmed in the study has access to consultation by a clinical specialist.	0. No Why? 1. Yes	Nominal, dichotomous

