5.10 Data Analysis Plan

Descriptive analysis will be performed for all variables of interest proposed in this study. Descriptive statistics (frequencies and percentages) will be estimated. For continuous quantitative variables, measures of central tendency (mean and median) and measures of dispersion (variance, standard deviation) will be estimated. Possible relationships between sociodemographic variables, risk factors, and documentation of positive HCV antibodies will be explored, for which a bivariate analysis will be performed using X² (chi-square) tests to explore the proposed associations. All analyses will be performed with Stata version 18.

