5.11 Tools to be used

A form will be used to collect demographic data and the variables to be studied (Annex 1).

6 Ethical considerations

This protocol will be submitted for review and evaluation by the Research Ethics Committee in each of the participating institutions to obtain the respective approval for its execution.

The study is by the provisions of Resolution 8430 of 1993 of the Colombian Ministry of Health, according to article 11 numeral b, is classified as minimal risk, given that data records were used through common procedures consisting of a sample collection (blood) by capillary puncture. In addition, the criterion of respect for the dignity and protection of the rights and welfare of the participants will prevail.

Informed consent will be requested in written form to all participants, giving clear and easily understandable information about the objectives of the research. The consent will be explained and doubts about it will be resolved, and complete freedom will be given to withdraw consent at any time during the study, for the reasons that the subject considers (Annex 2).

The study will be coordinated by health professionals and the sampling and data collection will be performed by trained nursing assistants. The confidentiality of the data collected will be guaranteed, the information obtained will not be used for purposes other than the current research process, and at the time of disclosure of the information, sensitive data or data that allow the identification of the participating individuals will not be published, the rules outlined in the law 1581 of 2012 on habeas data will be followed.

None of the authors have conflicts of interest to declare.

7 Expected results & impact

Strengthening of the scientific community

Expected Result/Outcome	Indicator	Beneficiary
Screening adults with risk factors for hepatitis C	The proportion of people diagnosed with hepatitis C	Users affiliated with the SGSSS, benefit plan administrators, and health personnel.
Linkage to treatment of confirmed positive cases for HCV infection in the hospitals included in the study.	The proportion of people diagnosed with chronic hepatitis C who started treatment	Users affiliated with the SGSSS, benefit plan administrators, and health personnel.

Social appropriation of knowledge

Expected Result/Output	Indicator	Beneficiary

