12.1 Annex 1. Data collection instrument

Adult screening for hepatitis C and linkage to treatment in Colombian hospitals	
Patient's name:	Identification number:
Age (in years):	Sex: Male: ___ Female: ___
Contact phone number:	Residence address: Department of Residence: Municipality of residence:
Affiliation scheme: 0. Uninsured: _____ 1. Subsidized: _____ 2. Contributory: _____ 3. Special: _____ 4. Exception: _____	Institución prestadora de servicio de salud (IPS): Fundación cardiointantil _____ Fundación Santafé _____ Clínica Colombia _____ Hospital Universitario San Ignacio _____ Fundación Valle de Lili _____ Hospital Pablo Tobón Uribe _____ Hospital Universitario Julio Méndez Barreneche E.S.E. _____
E-mail: _____ Nationality: _____	
Received blood transfusion before 1996: YES ___ NO ___	Year of transfusion:
Name of EAPB or Entity obliged to compensate:	Major Surgery: Yes ___ No ___ Type of surgery: Abdominal laparotomy: Yes ___ No ___ Gynecologic surgery of any type: Yes ___ No ___ Orthopedic surgery of any type: Yes ___ No ___ Any surgery that has required post-procedure in-hospital surveillance: Yes ___ No ___
Tattoos: Yes ___ No ___	Intravenous drug user: Yes ___ No ___ Nasal drug user: Yes ___ No ___
Man who has sex with men: Yes ___ No ___	Known hepatitis B virus infection: Yes ___ No ___
Known HIV infection: Yes ___ No ___	Have you ever had tattoos or body piercings? Yes ___ No ___
Abnormal liver tests or with liver disease:	Healthcare workers or members of public

Yes__ No__	safety (e.g., correctional service officers or police) who have come into contact with blood at work through needle sticks or sharps injuries: Yes__ No__
A person who has undergone hemodialysis: YES__ NO__	Diagnosis of diabetes: YES__ NO__
Diagnosis of Cryoglobulinemia: YES__ NO__	Diagnosis of coronary artery disease: YES__ NO__
Diagnosis of renal failure: YES__ NO__	
Population deprived of liberty or previously incarcerated persons: YES __NO__	
HCV antibody detection test: Non-reactive: _____ Reactive: _____	
Viral load test: Positive: _____ Negative: _____ Not applicable: _____(in all cases where HCV antibody screening test is non-reactive).	
Case reported to Sivigila YES__ NO__	
The positive case has been followed up YES __NO__	
The patient has had access to a specialized consultation YES __NO__ Why?	
The patient was able to access treatment YES __NO__ Why?	
Date of completion:	
Name of the person doing the diligence:	

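### Annex 1 lacks fields for seven of the 11 diseases in the comorbidity variable, for doctor visits, and for prior HCV cure

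*Combined protocol and SAP*

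**What the plan says.** Section 5.11 of the protocol ties the variables to one instrument: "A form will be used to collect demographic data and the variables to be studied (Annex 1". Section 5.9 has the same form completed for each consenting eligible person.

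Table 1 of 5.5 (not the sample-size table in 5.8, which carries the same number) defines a single yes/no variable for comorbidities potentially associated with HCV. Its list includes "Hypothyroidism, Flat lichen, Rheumatoid arthritis, Non-Hodgkin's lymphoma, Acute lymphoblastic leukemia, Waldenstrom's macroglobulinemia", along with diabetes, ischemic heart disease, cryoglobulinemia, chronic renal failure and Sjögren's syndrome. The 5.3 list of qualifying comorbidities for people under 50 has the same diseases plus HIV; it includes "hypothyroidism, lichen planus, rheumatoid arthritis, HIV, non-Hodgkin's lymphoma, acute lymphoblastic leukemia". Annex 1 asks for single diagnoses, such as "Diagnosis of Cryoglobulinemia".

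Table 1 also has one variable in its missed-opportunity category: "Doctor visits in the last month".

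On earlier HCV infection, 5.3 admits "Individuals previously treated for HCV with sustained viral response in whom reinfection is suspected". Section 5.4 excludes people with proven cure who have no risk behaviors for reinfection.

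The analysis that uses the risk factors is in 5.10: "Possible relationships between sociodemographic variables, risk factors, and documentation of positive HCV antibodies will be explored", by bivariate chi-square tests.

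**The concern.** If the form that supplies the data lacks a field, the variable is either left out or derived wrongly.

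For the comorbidity variable the second is the likelier outcome. An analyst who derives it from the available fields will code as unexposed anyone whose only listed disease is one that the form does not ask about. That puts exposed people into the comparison group of the exploratory analysis, and nothing in the dataset would reveal it.

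The number of doctor visits could not be reported at all. For prior cure, the dataset could not show whether a given participant belonged to the group admitted by 5.3 or the group excluded by 5.4.

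**Working it through.** The plan states no figure on this point, so the check is a field-by-field comparison of 5.3, Table 1 of 5.5 and Annex 1.

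**Comorbidity variable.** Table 1 lists 13 entries. Chronic renal disease (as failure and as insufficiency) and Sjögren's syndrome each appear twice, so 13 − 2 = 11 distinct diseases. Section 5.3 lists 12: the same 11 plus HIV. Table 1's flat lichen is read as lichen planus.

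| Disease | Table 1 | 5.3 | Annex 1 field |
|---|---|---|---|
| Diabetes | yes | yes | yes |
| Ischemic heart disease | yes | yes | yes, as coronary artery disease |
| Cryoglobulinemia | yes | yes | yes |
| Chronic renal failure | yes | yes | yes, as renal failure |
| Sjögren's syndrome | yes | yes | no |
| Hypothyroidism | yes | yes | no |
| Lichen planus | yes | yes | no |
| Rheumatoid arthritis | yes | yes | no |
| Non-Hodgkin's lymphoma | yes | yes | no |
| Acute lymphoblastic leukemia | yes | yes | no |
| Waldenström's macroglobulinemia | yes | yes | no |
| HIV | separate variable | yes | yes, own item |

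Against Table 1, 11 − 4 = 7 diseases have no field. Against 5.3, 12 − 5 = 7, and they are the same seven. Annex 1 has no overall comorbidity item and no other-disease item that could stand in for them.

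**Effect on the chi-square analysis.** Let e be the share of participants with any of the 11 diseases, and m the share of those who have only diseases from the missing seven. Let p7 be the antibody-positive proportion in that last group, and p0 the proportion in people with none of the 11. The form-derived unexposed group then has the proportion

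[(1 − e)·p0 + e·m·p7] / [(1 − e) + e·m]

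instead of p0. If p7 exceeds p0, the comparison group looks more positive than it is, and its contrast with the remaining exposed group shrinks. If p7 is below p0, the reverse holds. The documents give none of e, m, p7 or p0, so neither size nor direction can be calculated. The four diseases on the form can still be tested singly.

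**Doctor visits.** Table 1 asks for a count. Annex 1 has no such field.

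**Prior HCV treatment or cure.** It is needed by one inclusion route in 5.3 and one exclusion in 5.4. Annex 1 has no field and Table 1 has no variable.

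**Smaller gaps.**
- Scarification is in 5.3 and Table 1. The form asks about tattoos and then "Have you ever had tattoos or body piercings", with no mention of scarification.
- Students with occupational blood exposure are in 5.3, but neither in Table 1 nor on the form.
- Medical or dental intervention is in 5.3, but neither Table 1 nor the form has a general item. Major surgery, transfusion before 1996 and hemodialysis are recorded and cover part of it.

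**The case against.** The strongest reply is that eligibility is settled before the form is opened: 5.9 has it completed for people who already meet the criteria. Not recording each entry route does not mean that eligibility went unchecked. That stands. The prior-cure gap is a failure of verifiability from the data, not evidence of wrong enrolment. People over 50 qualify by age, so the other unrecorded routes matter only for younger participants.

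A second reply is that the tablet-based case report form may hold more than Annex 1. The available text describes no other variable list, and 5.11 names Annex 1.

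Third, the comorbidity variable serves only an exploratory bivariate analysis, and being a single 0/1 variable it could be restored with one form item. Both statements are correct. They limit the consequence and the minimum remedy, but they do not remove the mismatch.

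A reader might also infer that the undated yes/no fields for specialist consultation and treatment are part of the same mismatch. They are not. Table 1 records both as yes/no too, the specific objective in 4.2 is to count who gained access, and section 7 uses a proportion. The expected-impact row on time from PCR diagnosis to treatment concerns the years after the project, and its indicator is a number of people. Nor can one say that the plan has no data cut-off, because part of the text between sections 9 and 12 was not available for this review.

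The national follow-up figures in section 2 might seem to show bias from unequal follow-up: 584/634 = 92.1% treated in the 2019 cohort against 219/326 = 67.2% in the 2020 cohort, a gap of 24.9 points. The arithmetic is right, but no follow-up times are given for either cohort, other causes may contribute, and the gap says nothing about the missing form fields.

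**Conclusion.** The point holds as an inconsistency between the form and the protocol. Annex 1 omits seven of the 11 diseases in the Table 1 comorbidity variable and the only missed-opportunity variable. Neither Annex 1 nor Table 1 captures the prior-cure information that separates a 5.3 inclusion from a 5.4 exclusion.

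The count of seven is lenient: it accepts coronary artery disease as ischemic heart disease and renal failure as chronic renal failure. It assumes that the working form has no fields beyond those printed in Annex 1.

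The consequences are a comorbidity variable that would be miscoded if derived from the form, one Table 1 variable that cannot be reported, and one eligibility boundary that cannot be audited from the data. It would be wrong to infer that the main result is compromised: antibody and viral-load results are both on the form, and the primary prevalence estimate is not affected. The point should be corrected because the repair is cheap and data not collected at screening are hard to recover. It does not threaten the study's main aim.

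**What to change.** In Annex 1:
- add the seven missing diseases, preferably as single yes/no fields, or at minimum as one comorbidity item listing every Table 1 disease;
- add the number of doctor visits in the last month;
- add prior HCV cure with suspected reinfection;
- add scarification and students to the existing items, and a medical or dental intervention item.

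In Table 1 of 5.5, remove the two repeated diseases, add the variables it lacks (prior cure, students, medical or dental intervention), and state that the comorbidity variable is derived from the form fields.

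The cost is a form and database update and slightly longer data entry. Anyone already enrolled would have the new fields missing unless they are recovered from records. Sample size and testing do not change.

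An optional improvement, separate from the inconsistency, is to record the dates of the RNA result, specialist visit and treatment start for antibody-reactive cases, and to report the proportion treated together with the follow-up time available.
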